11.1 Data confidentiality

Computer-based files will only be made available to personnel involved in the study through the use of access privileges and passwords. Wherever feasible, identifiers will be removed from study-related information. Precautions are already in place to ensure the data are secure by using passwords and HIPAA-compliant encryption.

11.2 Subject confidentiality

Data on clinicians and patients will be obtained from Epic. Any information that is obtained will be used for research purposes only. Information on patients will only be disclosed within the study team and to the patient's PCP. All study staff will be reminded of the confidential nature of the data collected and contained in these databases.

Information about study subjects will be kept confidential and managed according to the requirements of the Health Insurance Portability and Accountability Act of 1996 (HIPAA). No source documents will be printed or maintained in paper form at the study sites. Operational data used for daily study management will be stored on a secure drive maintained behind the University of Pennsylvania Health System (UPHS) firewall. Analytic data will be stored within Penn Leonard David Institute's Health Services Research Data Center (HSRDC). HSRDC is maintained at a high-security level in accordance with federal regulations governing secure computer systems (e.g., the Federal Information Security Management Act-FISMA). The Way to Health (W2H) platform servers are based in the University of Pennsylvania Digital Academic Research Transformation (DART). The DART provides a secure computing environment for a large volume of highly sensitive data. DART requires all users of data or applications on DART servers to complete a DART-hosted cybersecurity awareness course annually, which stresses federal data security policies under data use agreements with the university. Curriculum includes HIPAA training and covers secure data transfer, passwords, computer security habits and knowledge of what constitutes misuse or inappropriate use of the server. W2H uses a role-based access control (RBAC) approach to assure that participant confidentiality and study integrity is preserved. Access is granted by invitation only and can be revoked at any time. The W2H Team are employees of the University of Pennsylvania and Penn Medicine. All W2H team members have completed HIPAA Security training and CITI Protection of Human Subjects Research Training - ORA. Access to the backend database is restricted and only available to a select group of developers. The database is accessible only via a secure VPN (Virtual Private Network) and cannot be accessed from the public internet at all, i.e. authorized users can only access the databases from within Penn's network and over a secure VPN channel. Data from participating sites will be transferred to Penn (the data coordinating center) according to the methods defined in a fully executed Data Use Agreement. All data will be covered under the appropriate Data Use Agreements between Penn Medicine, UW Medicine, and Lancaster General Health and follow strict security guidelines.

11.3 Subject privacy

All efforts will be made by study staff to ensure subject privacy. Data will be evaluated in a de-identified manner whenever possible.

11.4 Data disclosure

Information on patients will only be disclosed within the study team and to the patient's primary care clinician (to whom this information is already available).

11.5 Protected Health Information/Data Protection

- Name
- Street address, city, county, precinct, zip code, and equivalent geocodes
- All elements of dates (except year) for dates directly related to an individual and all ages over 89
- Telephone and fax numbers
- Medical record numbers

11.6 Data and safety monitoring

A Data and Safety Monitoring Board (DSMB) is an independent group of experts convened to protect the safety of research subjects and to ensure that the scientific goals for the project are being met. While this study presents very low risk, the DSMB will be appointed by and act in an advisory capacity to the National Institute on Aging (NIA) to monitor participant safety, data quality and to evaluate the progress of the study. The Data and Safety Monitoring Plan (DSMP) will be reviewed and approved by the DSMB prior to study start. Detailed information about safety monitoring and reporting can be found in the Manual of Operating Procedures (Section 11) and the Data and Safety Monitoring Plan.

11.7 Risk/benefit

11.7.1 Potential study risks

There are minimal risks to PCPs and patients in this trial. Ordering an annual flu vaccine is a standard of care for these patients. The only research-related activity is the randomization of participants to different behavioral nudge strategies to increase flu vaccination uptake. Potential risks include patient frustration with messaging or outreach, duplicate flu vaccination within the recommended interval, or reaction requiring emergency department or hospital care among those with a previously known allergy or overdose of vaccine. Risks will be minimized by excluding any patients for which this study could be unsafe, i.e. if they have a documented allergy to the vaccine or documentation in their medical record that they have already received their flu vaccine this season.

There is a risk of breach of data and confidentiality. To minimize the risk of breach of data and confidentiality, we will use secure, encrypted servers to host the data and conduct the analysis. Operational data used for daily study management will be stored on a secure drive maintained behind the University of Pennsylvania Health System (UPHS) firewall. Analytic data will be stored within Penn Leonard David Institute's Health Services Research Data Center (HSRDC). HSRDC is maintained at a high-security level in accordance with federal

regulations governing secure computer systems (e.g., the Federal Information Security Management Act-FISMA). The Way to Health (W2H) platform servers are based in the University of Pennsylvania Digital Academic Research Transformation (DART). Data from participating sites will be transferred to Penn (the data coordinating center) according to the methods defined in a fully executed Data Use Agreement. All data will be covered under the appropriate Data Use Agreements between Penn Medicine, UW Medicine, and Lancaster General Health and follow strict security guidelines.

11.7.2 Potential study benefits

Receiving an annual flu vaccine is important for public health and the health of the patients. The EHR could be utilized to identify eligible patients, and patients at high risk for not receiving the vaccine and deliver nudges to help improve vaccine completion rates. The knowledge gained on how to increase flu vaccination rates could be applied to other populations and implemented at other health systems. PCPs may benefit from receiving feedback on their performance and having the vaccine order automatically ordered to help streamline the ordering process and prevent extra burden.

BE IMMUNE: Behavioral Economics to IMprove and Motivate vaccination Using Nudges through the EHR

University of Pennsylvania

[name]

[name]

[name]

NCT#06057727

Statistical Analysis Plan

01/07/2025

Objectives

Our primary objective is to test the effectiveness of multicomponent, personalized EHR-based nudges to both clinicians and patients for increasing flu vaccination completion among eligible primary care patients.

Relevant Study Design Details

Randomization

Primary care clinics will be randomized 2:1 to either a nudge intervention or usual care arm using covariate-constrained randomization, stratified by health system (Penn, UW). For the clinic level randomization, the covariate-constrained randomization will aim to balance the distribution of clinician panel baseline flu vaccination completion rate, panel size, and panel risk. Panel size is defined as the number of patient visits from September 1, 2022 through February 28, 2023. Panel risk is defined as the proportion of a clinician's patients who meet at least one of the following criteria: age \geq 70 years, Non-Hispanic Black race, residence in lower income communities (lowest quartile according to zip code), or no documented history of flu vaccine in the year prior. Second, patients who have an eligible appointment at an intervention clinic and are identified as high-risk for not completing a flu vaccination will be further randomized using a 1:1 ratio at the patient level—stratified by clinic—to receive either an additional, intensification nudge (bi-directional texting) or the standard nudge intervention (standard text messaging).

Blinding

All investigators, statisticians, and analysts will be blinded during the randomization, intervention, and analysis phases. They will be unblinded at the end of the study analyses, after all outcomes have been obtained.

Outcomes

The primary outcome is flu vaccination completion during the first eligible primary care visit.

Secondary outcomes are flu vaccination completion within 3 months of the first eligible primary care visit and flu vaccination ordering. These patient-level outcomes will be coded as a 1 to indicate completion (or signed order) and 0 to indicate non-completion (or unsigned/cancelled order).

Statistical Analysis

The primary analysis for all primary and secondary outcomes will follow the intent-to-treat principle.

Sensitivity analyses (described later) will include per-protocol and other approaches to evaluate robustness to protocol deviations for some patients.

Analytical Plan for Primary and Secondary Outcomes

The primary analysis will fit generalized estimating equations (GEE) with a patient-level binary outcome indicating flu vaccination completion at the eligible primary care visit (primary outcome) and within 3 months (secondary outcome) of the eligible visit. We will fit a single GEE model to estimate the following: 1) effect of the clinic-level intervention (pended orders) only versus usual practice (main effect averaging over individually randomized bi-directional versus standard texting for high-risk patients at intervention clinics), and 2) effect of bi-directional vs standard text messaging amongst high-risk patients seen at intervention clinics, and 3) effect of the multicomponent intervention (pended orders and intensive texting for high-risk patients) compared to usual practice. These effects of interest are analogous to comparisons of intervention sequences embedded within Sequential Multiple Assignment Randomized Trial (SMART) designs. Therefore, we will adapt statistical methods commonly used for the analysis of data from SMART designs and use them to analyze data from the trial. More specifically, we will adapt the weighted and replicated approach that is used to compare embedded treatment sequences in SMART designs.¹

The weighted and replicated method is an analytic trick that allows for standard statistical software to be used to fit a single model for statistical estimation and inference regarding multiple effects of interest. Only high-risk patients seen at active intervention clinics are randomized to standard or intensive text messaging. Low-risk patients and all patients seen at control clinics are only exposed to the clinic-level randomized assignment. As a result, they do not have an individual-level randomized assignment in the analytic data set. To fit a single model, we must assign these individuals a value for the individual-level randomization. To do so, we first replicate their row of data and assign one of their records to standard messaging and the other to intensive messaging. However, after replicating these individuals, they will be over-represented in the analytic data set compared to high-risk, intervention clinic patients who received an individual-level randomized assignment and are therefore not replicated. To re-balance the representation in the pseudo-population created by replicating some patient observations, we weight each row by the inverse of the probability of receiving the observed value of the individual-level intervention. That is, patients who were truly randomized to standard or intensive texting will receive a weight of 2 (inverse of $\frac{1}{2}$) while each row of a patient whose record was replicated will receive a weight of 1 (since their intervention “assignments” were deterministic).

Once the replicated data set is created, we will fit the following GEE model to the patient-level binary outcomes using the observation weights mentioned above:

$$\text{logit} (\Pr(Y = 1 | A_1, A_2, X)) = \beta_0 + \beta_1 A_1 + \beta_2 A_1 A_2 + \beta_3^T X, \quad (1)$$

where A_1 is an indicator of whether the patient was seen at an active (1) or control (-1) clinic; A_2 is an indicator of intensive (1) or standard (-1) text messaging (patients who were actually randomized will have only one value for A_2 , while replicated patients will have one 1 and one -1); $A_1 A_2$ is the interaction between the patient’s cluster assignment and their individual-level assignment(s); and X is a vector of all other covariates we want to control for which will at minimum include mean-centered versions of the three variables used in the constrained randomization procedure: 1) clinic size (number of patient visits); 2) baseline clinic risk (proportion of panel deemed high risk); and 3) baseline clinic completion rate (proportion of panel with completed flu vaccination).

We will specify an independence working correlation when fitting the primary GEE model.

Although we expect some amount of correlation amongst observations within clinic, the replicated subject observations should be treated as independent. Fortunately, estimates from GEE models are robust to misspecification of the working correlation structure, meaning they are consistent for the true values even when the working correlation is specified incorrectly. Furthermore, when correlation amongst observations within clinic is low, the efficiency of using an exchangeable working correlation is similar to or worse than when using an independent working correlation. Since we will randomize 45 clinics, we will not use a small cluster correction.² We will use this approach for both the primary and secondary outcome analyses. Given model (1) with effect coding (i.e., -1 and 1 for levels of A_1 and A_2), we have the following:

1. The main effect of A_1 is $2\beta_1$ (i.e., the main effect of clinic-level nudges averaging over the differential effects of standard and intensive texting).
2. The main effect of A_2 given $A_1 = 1$ is $2\beta_2$. This is the comparison of text messaging intensity (standard versus intensive) given clinic-level nudges are active.
3. The comparison of clinic-level nudges with intensive texting versus control is $2\beta_1 + \beta_2$.
4. The comparison of clinic-level nudges with standard texting versus control is $2\beta_1 - \beta_2$.

We will test each of the four linear contrasts of the parameters estimated from the GEE model. We will use a Bonferroni correction for the first two contrasts, aligning with how the study was powered (i.e., two-sided significance level of 0.025 for the first two contrasts). We will consider contrasts 3 and 4 as exploratory, and thus we will not correct the corresponding p-values for multiple testing. Results will be reported on the odds ratio scale, including 95% confidence intervals. Confidence intervals for contrasts 1 and 2 will incorporate the Bonferroni correction used for the two tests.

Sensitivity Analyses to Evaluate Model Specifications

As a sensitivity analysis, we will restrict the data to high-risk patients at active clinics and estimate the main effect of intensive vs standard text messaging, specifying an exchangeable working

correlation within clinics. As another sensitivity analysis, we will use an exchangeable working correlation at the clinic level after duplicating each clinic's data, assigning one 1 and one -1 for patients without an individual-level assignment, and removing the record for each high-risk patient an intervention clinic corresponding to the opposite of the individual-level randomized assignment that was received. Duplicated clinics will be treated as independent while observations within clinic will be treated as exchangeable. In this way, duplicated records will be treated as independent. Using this approach, we will re-test the main effect of A_1 , i.e., $2\beta_1$, to evaluate sensitivity to specification of the working correlation. We will use a t-distribution with degrees of freedom equal to the number of clinics (47) minus the number of mean model parameters to construct a confidence interval for $2\beta_1$. If the interval does not include 0 (log odds ratio scale) we will reject the null and conclude there is a significant effect of clinic nudges compared to usual care.

Sensitivity Analyses to Evaluate Protocol Deviations

Patients observed in the first six weeks at Penn did not receive the full intervention due to a switch from using API (Application Programming Interface) to RPA (Robotic Process Automation). Specifically, patients at intervention clinics at Penn did not receive pended orders. In our primary analyses, we will include these patients as having received pended orders, following the intent-to-treat principle. In sensitivity analyses, we will repeat our analyses of primary and secondary outcomes after excluding this group who did not receive the full intervention. To mitigate any confounding effects of time (i.e., patients more likely to complete vaccinations earlier in the season) we will also exclude all Penn control arm patients during the first six weeks of the trial. Since this issue was not encountered at UW, all UW patients during this six week time period will be included in this per-protocol analysis.

Next, we will leverage this subset of intervention clinic patients who did not receive pended orders to estimate the effect of texting alone (standard texting versus control and intensive texting versus control) on completion at the day of eligible visit. We will also leverage this subset of patients to estimate the effect of ordering amongst low-risk patients who received text messaging as well as amongst high-risk

subjects who received either standard or intensive text messaging. There was a different subset of patients in intervention clinics who did not receive text messaging. We will utilize this group to estimate the effect of ordering alone versus control. These analyses will be exploratory, and their feasibility will depend on the number of patients in each group who did not receive the full planned intervention components. Analyses will mimic the approach specified for the primary and secondary outcomes (e.g., GEE, weighting and replicating when appropriate).

Analytical Plan for Exploratory Analyses

To examine the effect of the intervention on flu vaccination ordering, a GEE with a binary outcome indicating whether the pended order was signed or cancelled will be fit. The rates of flu vaccination completion will be compared between (1) usual care, (2) clinic level nudge only, and (3) clinic-level nudges with high-risk intensification using the same weighted and replicated approach described for the primary outcome and the mean model given in equation (1). We will again use an independence working correlation for these comparisons and perform sensitivity analyses to assess sensitivity to specification of the working correlation.

Exploratory subgroup analyses will examine the effect of the clinic-level nudge versus usual care among patients who are 1) identified as low-risk for completion and 2) identified as high-risk for completion, and 3) seen at Penn versus UW. For (1), we will restrict the data set to low-risk patients in the active and control clinics. Then, we will fit a GEE model with an indicator for clinic randomized assignment and variables used in the covariate constrained randomization. We will fit the model with a logit link and exchangeable working correlation. For (2), we will subset the data to patients deemed high-risk in both active and control arms, we will fit a GEE model with an indicator for clinic randomized assignment, indicator for individual-level randomized assignment, interaction between the clinic- and individual-level randomized assignments, and variables used in the covariate constrained randomization. We will use the weighted and replicated approach described previously, replicating each high-risk patient in the control arm and assigning them each a weight of 1 while assigning each high-risk patient in the

intervention clinics a weight of 2. We will fit the model with a logit link and independent working correlation. We will test the main effect of the clinic-level nudge and the main effect of standard versus intensive texting. We will test contrasts 1), 3), and 4). For investigating possible effect heterogeneity by health system, we will re-fit models for our primary and secondary outcomes separately on data from Penn and UW.

To investigate potential effect heterogeneity over time, we will fit GEE models for our primary and secondary outcomes with the addition of month and month-by-treatment interactions. The model will take the following form:

$$\text{logit} (\Pr(Y = 1 | A_1, A_2, T, X)) = \beta_0 + \beta_1 A_1 + \beta_2 A_1 A_2 + \beta_3 T + \beta_4 A_1 T + \beta_5 A_1 A_2 T + \beta_6^T X, \quad (2)$$

where T is a categorical variable indicating study month. We will use the weighted and replicated approach and an independent working correlation structure. We will first assess whether the effect of text messaging style differs over time. If we do not find evidence of effect heterogeneity for text messaging style, we will drop A_2 from the model and focus only on the effect of pended orders over time using the following model:

$$\text{logit} (\Pr(Y = 1 | A_1, A_2, T, X)) = \beta_0 + \beta_1 A_1 + \beta_2 T + \beta_4 A_1 T + \beta_5^T X, \quad (3)$$

Inference will focus on the interaction effect, β_4 , and we will not use any weighting or replicating to fit this model. We will fit this model using an independent working correlation.

Lastly, we will determine which high-risk intensification subgroups experienced the greatest benefits of the clinic- and individual-level nudges. Using the data set restricted to high-risk individuals, we will fit the following model:

$$\text{logit} (\Pr(Y = 1 | A_1, A_2, Z, X)) = \beta_0 + \beta_1 A_1 + \beta_2 A_1 A_2 + \beta_3 Z + \beta_4 A_1 Z + \beta_5 A_1 A_2 Z + \beta_6^T X, \quad (4)$$

where Z is a single, high-risk criteria. We will fit model (2) separately for each high-risk criteria which will allow us to determine which high-risk intensification subgroups experienced the greatest benefits of the clinic- and individual-level nudges. We will again use the weighted and replicated approach,

duplicating each control arm patient and assigning them a weight of 1 while assigning each intervention clinic patient a weight of 2. We will use an independent working correlation structure.

We now provide details about the interaction effects of interest. First, note that the main effect of A_1 amongst $Z = 1$ is:

$$\begin{aligned}\beta_0 + \beta_1 + \beta_2 A_2 + \beta_3 + \beta_4 + \beta_5 A_2 + \beta_6^T X - (\beta_0 - \beta_1 - \beta_2 A_2 + \beta_3 - \beta_4 - \beta_5 A_2 + \beta_6^T X) \\ = 2\beta_1 + 2\beta_4\end{aligned}$$

Similarly, the main effect of A_1 amongst $Z = 0$ is:

$$\begin{aligned}\beta_0 + \beta_1 + \beta_2 A_2 + \beta_6^T X - (\beta_0 - \beta_1 - \beta_2 A_2 + \beta_6^T X) \\ = 2\beta_1\end{aligned}$$

Thus, $2\beta_4$ captures the additional effect of A_1 amongst high-risk individuals with $Z = 1$ relative to those with $Z = 0$. We will test this quantity ($2\beta_4$) for statistical significance separately for each high-risk category. Next, note that the main effect of A_2 amongst $Z = 1$ setting $A_1 = 1$ (i.e., within intervention clinics) is:

$$\begin{aligned}\beta_0 + \beta_1 + \beta_2 + \beta_3 + \beta_4 + \beta_5 + \beta_6^T X - (\beta_0 + \beta_1 - \beta_2 + \beta_3 + \beta_4 - \beta_5 + \beta_6^T X) \\ = 2\beta_2 + 2\beta_5\end{aligned}$$

Similarly, the main effect of A_2 amongst $Z = 0$ with $A_1 = 1$ is:

$$\begin{aligned}\beta_0 + \beta_1 + \beta_2 + \beta_6^T X - (\beta_0 + \beta_1 - \beta_2 + \beta_6^T X) \\ = 2\beta_2\end{aligned}$$

Thus, $2\beta_5$ is the additional effect of A_2 amongst high-risk individuals with $Z = 1$ relative to those with $Z = 0$. We will test this quantity ($2\beta_5$) for statistical significance separately for each high-risk category. We will not correct for multiple testing in any of the effect modification exploratory analyses.

References

2. Liang, K.-Y., & Zeger, S. L. (2000). Longitudinal Data Analysis of Continuous and Discrete Responses for Pre-Post Designs. *Sankhyā: The Indian Journal of Statistics, Series B (1960-2002)*, 62(1), 134–148.

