5.1 Design

This study will be a multisite, cluster randomized, pragmatic trial to evaluate the effectiveness of personalized nudges to clinicians and patients, relative to a control, to increase flu vaccination rates among older adults in accordance with CDC guidelines. This will include clinician and patient level nudge interventions, with additional, intensified nudge interventions for patients identified as high risk for not receiving a flu vaccine.

This cluster randomized trial will randomly assign primary care clinics in a 2:1 ratio to either a nudge interventions or control arm using a covariate-constrained randomization.¹⁰ The intervention arm consists of a multi-component nudge intervention for patients and primary care providers (PCPs). Patients at high-risk for non-completion of the flu vaccine will be randomized to an additional intensification nudge (compared with the multi-component nudge intervention alone).

All patients scheduled for a visit at the clinics randomized to the intervention arm will receive a pre-visit text message sent via Way to Health (a HIPAA compliant, approved platform) that informs the patient the flu vaccine has been reserved for them at their upcoming visit. Those patients that do not have a cell phone in the EHR will receive automated voice recording (AVR). For the patient intensification nudge, we will focus on patient subgroups within the clinic intervention arm that were identified through our previous analyses as high risk for not receiving a vaccine: age ≥ 70 , Black race, residence in lower income communities (lowest quartile according to zip code), or no documented history of flu vaccine in the year prior. Patients who meet these criteria will be randomized 1:1 to receive an additional nudge via a bidirectional text messaging intervention versus no additional nudge. We will translate patient text messages for patients who require an interpreter according to their language preferences in the EHR. Translation will be available for Spanish and up to 4 additional languages based on site specific populations and technical capabilities. Our preliminary work identified the following five languages that account for 97.5% of the expected study sample: English, Spanish, Chinese, Vietnamese, and Russian.

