do not show up to the first scheduled clinician visit will be considered enrolled and included in the primary analysis.

--Power Calculations--

For the following power calculations, we used an adjusted Type I error of 0.025 to account for two comparisons: 1) clinic-level nudges versus usual care, and 2) intensification for high-risk patients versus no intensification within practices where clinic-level nudges are provided. Based on retrospective data from our health systems, we will have 85% power to detect a 7-percentage point difference in the flu vaccine completion rate for comparison #1. This calculation assumed N=48 participating clinics across the two sites, an average cluster size of n=1385 patients, and an intracluster correlation (ICC) of 0.02. For comparison #2, we will have at least 99% power to detect a 2-percentage point difference even if the rate of vaccination in the high-risk group is 50%, the most conservative rate with respect to power. This calculation assumed 1:1 individual-level randomization of n=1000 high-risk patients within each of N=32 clinics that will be randomized to receive clinic-level nudges. These power calculations used combined retrospective data from Penn and UW to estimate the average number of patients per clinic and the number of high-risk patients who will be randomized. We expect to have greater power for both comparisons at the replication site which comprises more clinics and patients.

--Statistical Analysis--

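### Model (1) fixes only three clinic-level covariates and leaves the rest of X open, so a modest precision gain for the texting contrast (contrast 2) is not secured

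*SAP*

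**What the plan says.** In the SAP, under Analytical Plan for Primary and Secondary Outcomes, one weighted and replicated GEE estimates both alpha-controlled contrasts. Of its covariates the SAP says that "X is a vector of all other covariates we want to control for", and it sets a floor of three mean-centred clinic variables: clinic size, baseline clinic risk and baseline clinic completion rate. No closed list appears elsewhere in the SAP.

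The protocol's Statistical Analysis text (section 9) differs. For the clinic-level comparison it names health system, clinic size and panel risk. For the intensification comparison it names clinic fixed effects, which would also reflect the stratified patient randomisation. The SAP floor contains neither health system nor clinic fixed effects, and it adds baseline completion rate.

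Both documents identify patient-level predictors. One high-risk criterion in the SAP's Randomization section is "no documented history of flu vaccine in the year prior"; the others are age 70 or over, Non-Hispanic Black race and a lowest-quartile-income ZIP code. On timing, the SAP's section on protocol deviations describes "patients more likely to complete vaccinations earlier in the season". Risk status must be known before a patient can be randomised to texting, and appointment and vaccination data are extracted (protocol section 8.2). The SAP uses month in exploratory model (2) and each risk criterion in exploratory model (4), but commits to none of them in model (1).

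**The concern.** Contrast 2 compares patients randomised 1:1 within the same clinic. A variable that takes one value per clinic cannot account for differences between patients in that clinic, so the compulsory covariates do nothing for its within-clinic variance. Prior-season vaccination and visit month could, at no data-collection cost.

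The open wording matters too. Several covariate sets satisfy the SAP as written, and each would give its own p-value for the two contrasts tested at 0.025. The SAP is dated 01/07/2025 and describes the first six weeks at Penn in the past tense, so it was written after the intervention had begun. At stake are a few points of power for contrast 2 and certainty about which model is primary.

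**Working it through.** **Inputs from the documents.** Alpha: "we used an adjusted Type I error of 0.025 to account for two comparisons" (protocol, Power Calculations), and "two-sided significance level of 0.025 for the first two contrasts" (SAP), so z = 2.241. Contrast 2: 32 clinics × 1,000 high-risk patients = 32,000, or 16,000 per arm; 2 points at a 50% rate; stated power at least 99%. Contrast 1: "we will have 85% power to detect a 7-percentage point difference in the flu vaccine completion rate for comparison #1", assuming "N=48 participating clinics across the two sites, an average cluster size of n=1385 patients, and an intracluster correlation (ICC) of 0.02", with 2:1 allocation (32 versus 16 clinics). The control rate is not given.

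**Step 1. The plan's own figures.**
- Contrast 2: SE = √(0.5/16,000) = 0.00559; 0.02/0.00559 = 3.578; power = Φ(3.578 − 2.241) = 90.9%. The stated 99% is not reproduced. With 32,000 per arm the result is 99.8%, so the inputs may have been read as 1,000 per arm per clinic. That discrepancy is a separate matter; 90.9% is the baseline here.
- Contrast 1: design effect = 1 + 1,384 × 0.02 = 28.68. A two-proportion test on the deflated sample gives 86.8%, 84.6% and 83.2% at control rates of 30%, 35% and 40%, with a low of 82.6% near 46.5%. The stated 85% is reproduced for some control rates.

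**Step 2. Predictor strength (assumed).** The documents give no effect sizes. Take half the patients as vaccinated in the prior season and completion rates a (not vaccinated) and b (vaccinated). Then R² = 0.25(b − a)² / [μ(1 − μ)], where μ is the mean of a and b.
- 40% versus 50%: 0.0025/0.2475 = 1.0%
- 30% versus 60%: 0.0225/0.2475 = 9.1%
- 20% versus 60%: 0.04/0.24 = 16.7%

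**Step 3. Contrast 2 after adjustment.** Power = Φ(0.02/√(0.5(1 − R²)/16,000) − 2.241), carrying each R² over to the 50% setting.

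| R² | 0.02/SE | Power |
|---|---|---|
| 0 | 3.578 | 90.9% |
| 1.0% | 3.596 | 91.2% |
| 9.1% | 3.752 | 93.5% |
| 16.7% | 3.919 | 95.3% |

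Reaching 99% by adjustment alone would need R² of about 0.39.

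This is a two-sample approximation, not model (1), so it was checked by simulation. In simulated GEE fits, relative efficiency for contrast 2 was 1.05, 1.14 and 1.24 at R² of 0.035, 0.13 and 0.21, against 1/(1 − R²) = 1.04, 1.15 and 1.27. In the weighted and replicated model (1) itself, the contrast 2 z-statistic rose by about 0%, 6–8% and 8–11% from weak to strong predictors, and contrast 1 was essentially unchanged.

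**Step 4. Contrast 1.** The within-clinic share of its variance is (1 − 0.02)/28.68 = 3.4%. Patient-level R² of 0.10, 0.20 and 0.30 therefore cuts the variance by 0.3%, 0.7% and 1.0%. At a 46.5% control rate, power (unpooled formula) moves from 82.7% to 82.9%, 83.0% and 83.2%.

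In simulation at an ICC of about 0.02 (assumed odds ratios of 4 for prior vaccination and 0.8 per month), relative efficiency was 1.00–1.03 when clinics did not differ in case mix. When they did, and baseline completion rate was in the model, it ranged from about 0.7 to 1.9. Large gains appeared only when case mix drove most of the ICC and the baseline rate was a poor proxy.

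**The case against.** The strongest reply is that the SAP sets a floor, not a ceiling. Patient-level covariates are not excluded, so whether precision is lost depends on what is added. That stands: the defect is that nothing secures the gain, not that the plan rules it out.

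A reader might infer that precision is being lost across the primary analysis. The documents do not support this for contrast 1. Nearly all of its variance is between clinics, and baseline completion rate and panel risk, the latter built from the same four patient criteria, are already balanced in the randomisation and included in X. Adjustment could even cost efficiency there.

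A reader might also take the predictors to be strong. The documents name risk groups and remark on season, without effect sizes. With weak predictors the gain is about 0.3 points.

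Post-hoc choice is partly guarded against, since both documents blind investigators, statisticians and analysts through analysis. That lowers the risk but does not say which model is primary. Blinding may also be fragile here: replicated control patients carry two rows of weight 1, while randomised patients carry one row of weight 2, so the data structure can reveal the active clinics unless it is masked.

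Finally, covariate adjustment on the logit scale changes the estimand. In one simulated scenario the contrast 1 odds ratio moved from 1.30 to 1.35 and its SE from 0.062 to 0.071, with almost no change in z. That stands, and it argues against imposing one patient-level X on both contrasts.

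**Conclusion.** The point holds for contrast 2 and for the open covariate list. The plan commits to covariates that cannot reduce within-clinic variance in an individually randomised comparison, and leaves unnamed the patient data that could. The likely gain is modest: from 90.9% to between about 91% and 95% power. It rests on assumed R² of 1% to 17%, a 50% vaccination rate, a 2-point effect, 16,000 patients per arm and a two-sample approximation. It carries somewhat more weight because the protocol's inputs give about 91% power, not 99%. For contrast 1 no material gain should be claimed. Nothing here biases either contrast; the matter is efficiency and pre-specification.

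**What to change.** Before unblinding, replace the open definition of X with a closed list.

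- **Both contrasts:** the three clinic covariates and health system, reconciled with the protocol's Statistical Analysis section.
- **Contrast 2:** add patient prior-season vaccination, the age, race and low-income ZIP criteria, and month of eligible visit. State whether the protocol's clinic fixed effects are retained, and reconcile the two documents.
- **Contrast 1:** keep the clinic-covariate fit as primary, with the patient-adjusted fit as a sensitivity analysis.
- **Reporting:** beside the adjusted contrast 2 odds ratio, which is conditional, give a standardised marginal odds ratio or risk difference with clinic-clustered standard errors.

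No new data are needed. The cost is SAP wording, one extra sensitivity fit, and a standardisation step whose standard errors must respect the weighting, replication and clustering. Because the two contrasts would no longer share one covariate set, the SAP's statement that a single model yields every effect needs amending.
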